5. TREATMENT

5.1 Overview

The study will enroll patients with CLL and NHL in a dose escalation and subsequent expansion. First, patients with relapsed or refractory disease will be enrolled in a dose finding study that will assign doses for each patient using a modified continuous reassessment method using software developed by Piantadosi (Modified Continual Reassessment Method, version 4.0). Up to 10 patients with CLL and 10 patients with NHL will be treated at the estimated MTD as part of the expansion.

In August 2016 after 2 patients were treated at dose level 2 for 1 cycle, both reported significant fatigue and anorexia. While not technically DLT, these AEs were concerning to the investigators, and after discussion with the DSMC it was decided to return to dose level 1 for continued expansion. This was discussed with Karyopharm, who reported increased tolerability

and efficacy using once weekly dosing strategies in other studies.

Cohort 3, which will initiate after the dose escalation and expansion, will add selinexor administered weekly (days 1, 8, and 15 of each cycle) at 40 mg PO, to patients receiving ibrutinib as frontline therapy for at least 12 months. Selinexor plus ibrutinib will be administered for 14 cycles, with discontinuation of selinexor after 14 cycles. At the end of 14 cycles, patients who achieve a minimal residual disease (MRD) negative response may have both drugs discontinued at the discretion of the treating physician. Patients who are MRD positive at the end of 14 cycles will discontinue selinexor and are recommended to continue ibrutinib.

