Grade 3 without bleeding	
Rule out other causes including drug effects.
 
For first occurrence: skip 1 dose and reduce selinexor by 1 dose level.
 
If recurrent, unless contraindicated, start treatment with moderate to high doses of thrombopoietin stimulating agents such as romiplostim 5 to 10 µg/kg SC weekly (preferred) or eltrombopag 100 to 150 mg QD.
 
In cases where there is significant disease involvement in the bone marrow or pre-existing compromised marrow function (eg, due to prior marrow-toxic therapy), or if there is baseline thrombocytopenia Grade 2-4 at baseline, the Investigator in consultation with the Medical Monitor may decide to continue selinexor dosing without dose reductions and/or interruptions as specified above, provided that platelet counts and bleeding symptoms/signs are closely monitored. Thrombopoietin stimulating agents are recommended.

Grade 4 without bleeding	
Rule out other causes including drug effects.
 
Interrupt selinexor until patient recovers to Grade 2 or baseline. Selinexor dosing may be reduced by 1 dose level (it is recommended to have only 1 dose modification per cycle).
 
If recurrent, unless contraindicated, start treatment with moderate to high doses of thrombopoietin stimulating agents as above.
 
In cases where there is significant disease involvement in the bone marrow or pre-existing compromised marrow function (eg, due to prior marrow-toxic therapy), the Investigator in consultation with the Medical Monitor may decide to continue selinexor dosing without dose reductions and/or interruptions as specified above, provided that platelet counts and bleeding symptoms/signs are closely monitored.

Grade ≥ 3 with bleeding	
Interrupt selinexor dosing and check platelet counts weekly until the bleeding has stopped, patient is clinically stable and the platelets have recovered to Grade 2 or baseline. When resuming selinexor, reduce by 1 dose level.
 
If recurrent, unless contraindicated, start treatment with moderate to high doses of thrombopoietin stimulating agents as above.

Neutropenia	

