≥ Grade 3	
Hold until neutrophils, hemoglobin, or platelets have returned to within 50% of pretreatment values. If initial value is within 50% of pretreatment value, no hold is needed.
 
 • 1st occurrence: No change in dose • 2nd occurrence: Cohort 1 and 3= No change in dose; Cohort 2 = Decrease ibrutinib to the next lowest dose level. • 3rd occurrence: Decrease ibrutinib to the next lowest dose level. • 4th occurrence: Patient comes off study 	
Hold until neutrophils, hemoglobin, or platelets have returned to within 50% of pretreatment values. If initial value is within 50% of pretreatment value, no hold is needed.
 
 • 1st occurrence: No change in dose. Initiate granulocyte colony-stimulating factors for grade >3 neutropenia. • 2nd occurrence: Decrease selinexor to next lowest dose. • 3rd occurrence: No change in dose • 4th occurrence: Decrease selinexor to the next lowest dose • 5th occurrence: No change in dose • 6th occurrence: Discontinue selinexor

*Dose reductions < ibrutinib 140mg daily or selinexor 20 mg weekly are not permitted.
 
Recommendations:
 
 -Full supportive care, growth factors, and transfusions should be given as medically indicated. - If the patient tolerates a reduced dose for two cycles, patient may be dose escalated to the dose they received prior to the reduction after authorization from Principal Investigator. 		

Event Name	Bleeding	
Grade of Event	Management/Next Dose Ibrutinib*	Management/Next Dose of Selinexor*
≤ Grade 2 (mild to moderate)	
Hold ibrutinib for at least 7 days after last bleeding and until platelets return to ≥ 50% of baseline value.
 
 • 1st occurrence: Restart ibrutinib at next lowest dose level. In cases where no bleeding is observed after 6 days of dosing return to full dose at the physician's discretion. • 2nd occurrence: Restart ibrutinib at next lowest dose level. • 3rd occurrence: Patient comes off study. 	
Hold selinexor for at least 7 days after last bleeding and until platelets return to ≥ 50% of baseline value.
 
 • 1st occurrence: Restart selinexor at next lowest dose level. In cases where no bleeding is observed after 6 days of dosing return to full dose at the physician's discretion. • 2nd occurrence: Restart selinexor at next lowest dose level. • 3rd occurrence: Patient comes off study.

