Grade 2 or 3	Hold until therapeutically anticoagulated and platelets are \geq 50,000/mm ³ . Resume at the same dose level.	Hold until therapeutically anticoagulated and platelets are \geq 50,000/mm ³ . Resume at the same dose level.
Recommendation: Anticoagulation (warfarin prohibited)		

Event Name	Hyponatremia	
Grade of Event	Management/Next Dose Ibrutinib	Management/Next Dose of Selinexor
Grade 1 (Lower Limit of Normal to 130 nM)	No change in dose	Maintain selinexor dose and frequency level, assure adequate fluid, electrolyte and caloric intake, adjust other medications, and consider salt supplementation 1-3 times per day. Correct sodium level for hyperglycemia (serum glucose >150 mg/dL). Rule out other causes of low sodium (e.g., SIADH, cardiac, hepatic, adrenal, renal, and thyroid diseases, Fanconi Syndrome, diuretic use, etc.).
Grade 3 (126-129 mmol/L)	No change in dose	Ensure patient is euvolemic and has sufficient fluid and electrolyte intake. Replace fluids orally or IV if patient is dehydrated. Correct sodium level for hyperglycemia. Rule out other causes of low sodium (see above for Grade 1). Hold selinexor until hyponatremia

		resolves to Grade ≤ 1 (≥ 130 nM) and initiate aggressive salt supplementation 2-3 times per day. Restart at the same dose and frequency of selinexor and monitor serum sodium closely. If this recurs, measure urine sodium and creatinine levels to investigate for other causes of hyponatremia.
Grade 3 (120-125 mmol/L)	No change in dose	Hold selinexor dose until sodium ≥ 125 mmol/L*. Decrease selinexor to the next lowest dose level for initial and each subsequent occurrence.

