9.4.5 Site Performing Correlative Study: OSU CLL Experimental Therapeutics Laboratory

10. STUDY CALENDAR

Pre-study evaluations must be completed within 2 weeks of study registration, unless otherwise noted. Karyotype, FISH, bone marrow biopsy, peripheral blood immunophenotyping, and CT scans must be performed within 45 days of study registration. Informed consent must be obtained within the time frame specified by local policy. IgVH mutational status does not need to be repeated if performed previously. It is acceptable for individual cycles to begin \leq a 24-hour (business day) window before and after the protocol-defined date for Day 1 of a new cycle. For example, if the treatment due date is a Friday, the window for treatment includes the preceding Thursday through the following Monday. In addition, patients are permitted to have a new cycle of therapy delayed up to 7 days for major life events (e.g., serious illness in a family member, major holiday, vacation that cannot be rescheduled) without this being considered a protocol violation. New cycles of ibrutinib can be started up to 7 days before the protocol-defined date for major life events. Documentation to justify a delay or advance of a cycle should be provided. Additionally, all tests and observations associated with the beginning of a cycle may be performed up to 48 hours prior to beginning the cycle of therapy.

Calendar for dose escalation and expansion cohorts

General Study Calendar											
Cycle	Pre-Study	1				2-3		4-6	7+ ^k	Off Treatment	Follow-up ^l
Day		1	8	15	22	1	15	1	1		
Eligibility checklist	X										
Informed consent	X										
History ^a	X										
Progress note ^b		X	X	X	X	X	X	X	X	X	X ^l
Physical exam	X	X	X	X	X	X	X	X	X	X	X ^l
Ophthalmologic exam ^c	X									X	
Concurrent meds	X	X	X	X	X	X	X	X	X		
Vital signs/weight/height/BSA	X	X	X	X	X	X	X	X	X	X	
ECOG ^d	X	X	X	X	X	X	X	X	X	X	
CBC, dif, platelets	X	X	X	X	X	X	X	X	X	X	
Coagulation ^e	X	X	X	X	X	X	X	X	X	X	
Chemistry ^f , Ca, Mg, Phos	X	X	X	X	X	X	X	X	X	X	
Liver function tests ^g	X	X	X	X	X	X	X	X	X	X	
LDH	X	X				X					
Uric acid	X	X									
Peripheral blood immunophenotyping	X					X ^m		X ⁿ	X ^o	X	X ^l
Quant immunoglobulins	X										
SPEP with	X										

immunofixation											
CLL karyotype, FISH panel ^h & IgVH mutational analysis	X ⁱ										
Pregnancy test ^j	X										
HIV/Hep	X										
Buccal swab	X										
ECG	X										
Dispense KPT-330		X				X		X	X		
Adverse event evaluation	X	X	X	X	X	X	X	X	X	X	X ^h

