PET/CT or CT scans	X					X ^m		X ⁿ	X ^o	X	X ^h
Bone marrow biopsy and aspirate	X ^p							X ^q	X ^q		X ^q
Histologic review	X ^r										
Correlative studies	See Correlative Study Calendar										

- Initial medical history should include: baseline symptoms; a detailed history of prior cancer therapies including start and stop dates, disease progression during or after therapy, as well as discontinuations due to intolerability or any other serious illness; family and social history; calculation of Rai Stage (for CLL patients), MIPI (for MCL patients), or IPI (NHL patients other than MCL; see Appendix C).
- Progress notes should include: new symptoms or adverse events, ECOG performance status (Appendix A), documentation of physical exam, status of disease.
- Ophthalmologic exam: required at screening, if clinically indicated during study, and at final visit. Prior to dilation: best corrected visual acuity, visual field examination via automated perimetry, tonometry, and color vision test. Dilated funduscopy and slit lamp exam including anterior segment photos to document lens clarity.
- For ECOG performance status, see Appendix A
- Prothrombin time, international normalization ratio, and activated partial thromboplastin time
- Sodium, potassium, bicarbonate, BUN, calcium, chloride, creatinine
- Albumin, alkaline phosphatase, total bilirubin, total protein, SGOT [AST], SGPT [ALT]
- FISH panel will use probes to detect for abnormalities in chromosomes 13q, 12, 11q, and 17p.
- For CLL patients only.
- Pregnancy tests for females of childbearing potential. A female of childbearing potential (FCBP) is a sexually mature female who: 1) has not undergone a hysterectomy or bilateral oophorectomy; or 2) has not been naturally postmenopausal (amenorrhea following cancer therapy does not rule out childbearing potential) for at least 24 consecutive months (i.e., has had menses at any time in the preceding 24 consecutive months). Female of childbearing potential must have a negative serum β -Hcg pregnancy

test result within 3 days of first study dose.

- k. For cycles 7 and higher, patient will be required to return for evaluation and to receive KPT-330 every 3rd month (eg. Cycle 7 Day 1, Cycle 10 Day 1, Cycle 13 Day 1....)

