- l. Reassessment off therapy will occur 4 weeks from the last dose of study therapy. For patients removed from study for reasons other than disease progression, reassessment will then occur then every 6 months until progression or an alternative therapy is started.
- m. Cycle 2 Day 1 only.
- n. Cycle 4 Day 1 only.
- o. Restaging scans and immunophenotyping will be performed every 3 cycles for the first year and then every 6 months thereafter.
- p. Bilateral bone marrow biopsies are preferred for lymphoma patients.
- q. A bone marrow biopsy and aspirate should be performed to confirm a complete response if there was bone marrow involvement at diagnosis, clinical MRD flow should be performed in this case.
- r. For patients with DLBCL only: Paraffin block must be submitted for immunohistochemistry evaluation of CD10, bcl-6, and MUM-1 to determine ABC vs GCB subtype. Biopsy to confirm histologic review does not need to be repeated for pre-study requirements, so long as previously obtained tissue confirms patient meets histologic eligibility criteria prior to study registration.

OSU Protocol #:14087

Version 7

Date: 03 August 2021

Cohort 3 Study

Calendar

Cycle	Pre-Study	Day 1, Cycles 1-3	Day 1, Cycles 6, 9, 12	Cycle 14 Day 1	Day 1, every 3 cycles following cycle 14 (continue ibrutinib) C17, 20, 23, 26, etc.	Day 1, every 3 cycles following cycle 14 (off therapy)	Follow-up (off therapy) ^j
Eligibility checklist	X						
Informed consent	X						
History ^a	X						
Progress note ^b		X	X	X	X	X	X
Physical exam	X	X	X	X	X	X	X
Ophthalmologic exam ^c	X						
Concurrent meds	X	X	X		X		
Vital signs/weight/height/BSA	X	X	X		X	X	
ECOG ^d	X	X	X		X	X	
CBC, dif, platelets	X	X	X		X	X	
Coagulation ^e	X	X	X		X		
Chemistry ^f , Ca, Mg, Phos	X	X	X		X	X	
Liver function tests ^g	X	X	X		X		
LDH	X						
Uric acid	X						
Peripheral blood immunophenotyping	X		X			X	X
Quant immunoglobulins	X		X				
SPEP with immunofixation							

CLL karyotype, FISH panel ^h & IgVH mutational analysis ^h	X						
Pregnancy test ⁱ	X						
HIV/Hep	X						
Buccal swab	X						
ECG	X						
Adverse event evaluation	X	X			X		
PET/CT or CT scans	X					X ^k	X
Bone marrow biopsy and aspirate	X			X			
Correlative studies	X	X	X	X	X	X	

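### Cohort 3 has no calendar CBC, chemistry or liver test from Cycle 12 Day 1 to Cycle 17 Day 1 (140 days, nine selinexor doses), and none mid-cycle at any time

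*Combined protocol and SAP*

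**What the plan says.** Section 5.1 states that Cohort 3 "will add selinexor administered weekly (days 1, 8, and 15 of each cycle) at 40 mg PO", for 14 cycles. Section 5.2.3 gives a 28-day cycle.

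On the Cohort 3 calendar in section 10, the CBC, chemistry and liver function rows are ticked pre-study and in the columns "Day 1, Cycles 1-3" and "Day 1, Cycles 6, 9, 12". They are blank in the Cycle 14 Day 1 column, where the progress note, physical exam, marrow and correlative studies are ticked. The next ticks are every three cycles after Cycle 14, starting at Cycle 17. Patients continuing ibrutinib have all three rows ticked there. Patients off therapy have CBC and chemistry ticked, but not liver tests. The follow-up column (reassessment 4-6 weeks after the last dose, then every 6 months) ticks none of the three. Tests tied to the start of a cycle "may be performed up to 48 hours prior to beginning the cycle of therapy".

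The laboratory-triggered dosing rules still apply to this cohort. The ibrutinib column of section 6.1 names it ("Cohort 1 and 3= No change in dose"), and the selinexor column there makes no exception for it. Section 6.2 acts on sodium ("Hold selinexor dose until sodium").

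**The concern.** Several hold and reduce rules in sections 5.18, 6.1 and 6.2 are triggered by a laboratory value rather than a symptom. Section 8.1.5 lists thrombocytopenia, neutropenia and liver test changes among the selinexor safety considerations. In section 6.1 the action also depends on whether the event is a first, second or later occurrence, so an occurrence that no draw catches is not counted.

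The Cycle 14 Day 1 blank stands out because the patient is already there for an examination, a marrow and a correlative blood sample (section 9.2.2). At stake is whether a cytopenia, low sodium or transaminase rise late in selinexor treatment, or soon after it ends, is seen and acted on. The Cohort 3 toxicity summary (sections 13.3 and 13.8.1) would also miss what is not sampled.

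**Working it through.** The plan states no figure for this point; the check is calendar arithmetic.

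**Inputs.** Doses on Days 1, 8 and 15 of Cycles 1-14 (section 5.1); 28-day cycles (section 5.2.3); draws on Day 1 of Cycles 1, 2, 3, 6, 9, 12 and then 17 (section 10).

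**Formula.** Study day = 28 x (cycle - 1) + day. Planned doses = 14 x 3 = 42, the last on Cycle 14 Day 15 = 28 x 13 + 15 = day 379.

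| Draw | Study day | Days since previous draw | Doses since previous draw | Days since last dose |
|---|---|---|---|---|
| C1D1 | 1 | - | - | baseline |
| C2D1 | 29 | 28 | 3 | 14 |
| C3D1 | 57 | 28 | 3 | 14 |
| C6D1 | 141 | 84 | 9 | 14 |
| C9D1 | 225 | 84 | 9 | 14 |
| C12D1 | 309 | 84 | 9 | 14 |
| C17D1 | 449 | 140 | 9 | 449 - 379 = 70 |

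The 48-hour window makes the 14 days 12 to 14. The nine doses in the last row run from C12D1 to C14D15.

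**Mid-cycle.** There are 14 x 2 = 28 Day 8 and Day 15 doses, and 0 have a same-day draw. Six cycles have a Day 1 draw, so 6 x 2 = 12 of these doses follow a Day 1 value from their own cycle, on which section 6.1 can act. The other 28 - 12 = 16 fall in cycles with no calendar draw.

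**Counts taken for response.** Section 11.1 assesses response after 1 and 3 months, then every 3 months for a year. Suppose these are credited, together with a count at the end of Cycle 14. The longest CBC interval up to that last count is then 56 days if months mean completed 28-day cycles, or 84 days if the assessments coincide with Cycles 3, 6, 9 and 12. Every count so added is still 14 days after a dose. The CLL criteria in section 11.1.3 list no sodium, creatinine or liver test, so the 140 days stand for chemistry and liver tests.

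**After ticking C14D1** (study day 365): 365 - 309 = 56 days and 449 - 365 = 84 days. For liver tests in patients off both drugs, the 84 holds only if the C17D1-equivalent visit is ticked as well.

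**Optional Day 15 draw, illustration only.** Assume onset uniform over the 84 days of Cycles 1-3, an abnormality lasting d days, and a month-3 count credited at C4D1. The chance that a draw falls inside it is (number of draws x d)/84, for d no longer than the draw spacing.

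| d (days) | Now: 3 draws | With Day 15: 6 draws |
|---|---|---|
| 3 | 0.11 | 0.21 |
| 7 | 0.25 | 0.50 |
| 14 | 0.50 | 1.00 |
| 21 | 0.75 | 1.00 |
| 28 | 1.00 | 1.00 |

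Without the month-3 credit, which is the relevant case for chemistry and liver tests, d = 7 gives 2 x 7/84 = 0.17 now and 5 x 7/84 = 0.42 with Day 15 draws.

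**The case against.** Much of the sparseness is defensible. Cohort 3 patients have had at least a year of ibrutinib (section 3.1.1), have no ongoing Grade 3 or higher ibrutinib toxicity other than managed hypertension (section 3.2.15), and enter after escalation and expansion. Set against Cohorts 1 and 2, the scheduled draws after C1D1 up to C6D1 are 3 versus 10, but that comparison flatters the concern. Three of the seven extra draws (Cycle 1 Days 8, 15 and 22) lie in the DLT window, when patients not already on ibrutinib are also starting it. The only other mid-cycle draws are Day 15 of Cycles 2 and 3. From Cycle 7 that calendar is as wide as this one: "For cycles 7 and higher, patient will be required to return for evaluation and to receive KPT-330 every 3rd month". The 84-day intervals are therefore not peculiar to Cohort 3; the 140-day interval is.

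Unscheduled tests also exist. Section 7 requires laboratory monitoring in general terms, and section 5.18 lets selinexor continue through some thrombocytopenia "provided that platelet counts and bleeding symptoms/signs are closely monitored". Neither sets a time, and the weekly checks in section 5.18 start only once an event is known. This softens the gap without closing it.

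A reader might infer three stronger things that the documents do not support:

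- That no scheduled value informs any Day 8 or Day 15 dose. A Day 1 count is known before Day 8, and section 6.1 holds dosing on it.
- That a Cycle 14 Day 1 count supplies the MRD-negative CR endpoint. Section 13.5.4 sets that endpoint at the end of 14 cycles, with three doses still to come after the Day 1 count is drawn, and section 11.1.3 also requires CT, which is blank at that visit.
- That Day 15 is shown to be the right mid-cycle day. The documents give no nadir or recovery time.

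**Conclusion.** The point holds as a scheduling gap in safety laboratories. On the calendar, the last nine selinexor doses have no CBC, chemistry or liver test after Cycle 12 Day 1 until Cycle 17 Day 1: 140 days, ending 70 days after the last dose. In patients who stop both drugs, liver tests do not return at all. For CBC the gap may be shortened by counts taken for response; for chemistry and liver tests nothing else in the documents schedules a value. The absence of any mid-cycle draw is a lesser matter: it limits what is known of the current cycle's effect but does not disable the hold rules.

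The intervals assume 28-day cycles without delay; permitted delays lengthen them. How many events would be missed cannot be estimated from the documents. The cohort has ten patients, and DLT and MTD are unaffected. The change is worth making because it is nearly free.

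**What to change.** On the Cohort 3 calendar:

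1. Tick CBC with differential, chemistry and liver function at the existing Cycle 14 Day 1 visit.
2. Tick liver function at the first off-therapy visit after Cycle 14 (the Cycle 17 Day 1 equivalent), where CBC and chemistry are already ticked.

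Both use visits already on the calendar, so the cost is a few added tubes per patient.

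As an option for the sponsor, add a pre-dose Day 15 CBC, chemistry and liver draw in Cycles 1-3, with a local laboratory acceptable. That is 3 x 10 = 30 draws in all. Cohort 3 has no Day 15 visit, so each needs a short visit or a local order. It would give 3 of the 28 Day 8 and Day 15 doses a same-day value and leave the later 84-day intervals unchanged. If the sponsor holds nadir data, they should decide the day.

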11. MEASUREMENT OF EFFECT

11.1 Response Criteria

Response will be assessed by the International Working Group (IWG) Response Criteria for NHL patients⁴² and the International Workshop on CLL (IWCLL) criteria¹⁴ for CLL patients after 1 and 3 months of therapy, then every 3 months for 1 year, and then every 6 months thereafter until disease progression with no maximum treatment length.

11.1.1 Definitions

Evaluable for toxicity. All patients will be evaluable for toxicity from the time of their first treatment with selinexor.

Evaluable for response. Only those patients who have received at least four weeks of therapy and have had their disease re-evaluated will be considered evaluable for response. These patients will have their response classified according to the definitions stated below. (Note: Patients who exhibit objective disease progression prior to the end of 4 weeks will also be considered evaluable.)

